10.4.2. Treatment Emergent Flag for Adverse Events

Flag	Definition
Treatment Emergent	
 AEs will be considered emergent in the OLI, Injection and Follow-up Phase according to the classification defined in Table 5

10.5. Appendix 5: Data Display Standards & Handling Conventions

10.5.1. Reporting Process

Software

 The currently supported versions of SAS software version 9.4 will be used.
Analysis Datasets

 Analysis datasets will be created according to CDISC standards (SDTM IG Version 3.2 & ADaM IG Version 1.1).
Generation of RTF Files

 RTF files will be generated for all tables, listings, and figures in Appendix 10: List of Data Displays
Generation of xlm Files

 xlm files will not be generated.

10.5.2. Reporting Standards

General

 The current GSK Statistical Display Standards in the GSK Standards Library (IDSL) will be applied for reporting, unless otherwise stated (Library Location: https://spope.gsk.com/sites/IDSLLibrary/SitePages/Home.aspx): 
 4.03 to 4.23: General Principles 5.01 to 5.08: Principles Related to Data Listings 6.01 to 6.11: Principles Related to Summary Tables 7.01 to 7.13: Principles Related to Graphics Do not include participant level listings in the main body of the GSK Clinical Study Report. All participant level listings should be located in the modular appendices as ICH or non-ICH listings
Formats

 GSK Statistical Display Principles (5.03 & 6.06.3) for decimal places (DP's) will be adopted for reporting of data based on the raw data collected, unless otherwise stated. Numeric data will be reported at the precision collected on the eCRF. The reported precision from non eCRF sources will follow the GSK Standard Statistical Display Principles but may be adjusted to a clinically interpretable number of DP's.
Planned and Actual Time

 Reporting for tables, figures and formal statistical analyses: 
 Planned time relative to dosing will be used in figures, summaries, statistical analyses and calculation of any derived parameters, unless otherwise stated. The impact of any important deviation from the planned assessment times and/or scheduled visit days on the analyses and interpretation of the results will be assessed as appropriate. Reporting for Data Listings: 
 Planned and actual time relative to study drug dosing will be shown in listings (Refer to GSK Standard Statistical Display Principle 5.05.1). Unscheduled or unplanned readings will be presented within the participant's listings.
Unscheduled Visits

 Unscheduled visits will be assigned to a study visit using assessment windows defined in Section 10.3.

Descriptive Summary Statistics	
Continuous Data	Refer to GSK Standard Statistical Display Principle 6.06.1
Categorical Data	N, n, frequency, %
Graphical Displays	

 Refer to GSK Standard Statistical Display Principals 7.01 to 7.13. 	

10.5.3. Reporting Standards for Pharmacokinetic

Pharmacokinetic Concentration Data	
Descriptive Summary Statistics, Graphical Displays and Listings	
Refer to IDSL PK Display Standards. Refer to IDSL Statistical Principle 6.06.1.
 
For continuous data:
 
 Not quantifiable values (NQs) at the beginning of a participant profile (i.e., before the first incidence of a measurable concentration) are deemed to be zero as it is assumed that in this circumstance no drug is yet measurable in the blood. For NQs at the end of the participant profile (i.e., after the last incidence of a measurable concentration); 
 for individual plots and pharmacokinetic analyses these are dropped (set to missing) as they do not provide any useful information (and can erroneously indicate that absolutely no drug is present) for summary statistics, these are set to 0 (to avoid skewing of the summary statistics) Individual NQs which fall between two measurable concentrations are set to missing (individual values of this nature are assumed to be an anomaly) 
If two or more NQ values occur in succession between measurable concentrations, the profile will be deemed to have terminated at the last measurable concentration prior to these NQs. For the purpose of individual participant plots, these NQs will be set to 0, and the subsequent measurable concentrations will be retained. For the derivation of pharmacokinetic parameters, these NQs and any subsequent measurable concentrations will be omitted (set to missing).
 
Note: Concentration values will be imputed as per GUI_51487 for descriptive summary statistics/analysis and summarized graphical displays only.

Pharmacokinetic Parameter Data	
Descriptive Summary Statistics, Graphical Displays and Listings	
N, n, arithmetic mean, 95% CI of arithmetic mean, geometric mean, 95% CI of geometric mean, SD, SD of logged data, CVb (%), minimum and maximum will be reported.
 $CV_b (\%) = \sqrt{(\exp(SD^2) - 1) * 100}$ 
(SD = SD of Ln-Transformed data)

Untransformed PK parameter	tmax
PK parameter listed only	KALA, KALA lower, KALA upper, KALA no. of points, and Rsq_adjusted
Listings	Include the first point (KALA lower), last point (KALA upper) and number of points used in the determination of KALA (KALA no. of points), and Rsq_adjusted for listings.

10.6. Appendix 6: Derived and Transformed Data

10.6.1. General

Multiple Measurements at One Analysis Time Point

 • For non-ECG assessments: 
 ○ If there are multiple measurements within a time window (per Section 10.3), the value closest to the target day for that window will be used. If values are the same distance from the target, then the mean of the measurements (for quantitative parameters) or the worst-case of the measurements (for qualitative parameters) will be calculated and used in any derivation of summary statistics. • For ECG assessments, the average value (for quantitative parameters) or the worst-case value (for interpretation) from the triplicate assessments will be calculated and used in all of the summary statistics. • Only planned assessment timepoints (according to Appendix 2: Schedule of Activities) will be included in data displays summarizing measurements by visit. • Measurements at timepoints not selected for summarization by visit will be included in worst-case post-baseline determinations and in data listings. 
 ○ Worst-case post-baseline determination, details are outlined in the Programming Notes from Appendix 10: List of Data Displays. • Participants having both High and Low values for Normal Ranges at any post-baseline visit for vital sign measurements in the relevant Potential Clinical Importance summary tables.
Study Day

 • Calculated as the number of days from First Dose Date of CAB: 
 • Ref Date = Missing → Study Day = Missing • Ref Date < First Dose Date of CAB → Study Day = Ref Date – First Dose Date of CAB • Ref Date ≥ First Dose Date of CAB → Study Day = Ref Date – (First Dose Date of CAB) + 1

Period Day

 Calculated as the number of days from First Dose Date of CAB for the respective period (based on study period classifications in Table 5): 
Screening and OLI periods:
 
 If Assessment Date < First Dose Date of Oral CAB then 
 Period Day = Assessment Date – First Dose Date of Oral CAB If Assessment Date ≥ First Dose Date of Oral CAB then 
 Period Day = Assessment Date – First Dose Date of Oral CAB +1 
Injection 1 period:
 
 If Assessment Date < First Dose Date of Injection CAB then 
 Period Day = Assessment Date – First Dose Date of Injection CAB If Assessment Date ≥ First Dose Date of Injection CAB then 
 Period Day = Assessment Date – First Dose Date of Injection CAB +1 
Injection 2 period:
 
 If Assessment Date < Second Dose Date of Injection CAB then 
 Period Day = Assessment Date – Second Dose Date of Injection CAB If Assessment Date ≥ Second Dose Date of Injection CAB then 
 Period Day = Assessment Date – Second Dose Date of Injection CAB +1 
Follow-up period:
 
 If Assessment Date < Final Dose Date of Injection CAB then 
 Period Day = Assessment Date – Final Dose Date of Injection CAB If Assessment Date ≥ Final Dose Date of Injection CAB then 
 Period Day = Assessment Date – Final Dose Date of Injection CAB +1 
Where “Final Dose Date of Injection CAB” is the date of first CAB injection for participants who discontinue prior to receiving the second injection; otherwise this will be the date of the second CAB injection, if available.

10.6.2. Study Population

Age

 GSK standard IDSL algorithms will be used for calculating age where birth date will be imputed as follows: 
 Age, in whole years, will be calculated with respect to: 
 The participant's first dose date, if at least 1 dose of CAB was taken. The participant's first Screening visit, if the participant did not take any dose of CAB. For the purpose of calculating age, the '30th June' is imputed as the date and month of birth for all participants. Birth date will be presented in listings as 'YYYY'.
Body Mass Index (BMI)

 Calculated as Weight (kg) / [Height (m)²]
Oral CAB Exposure

 Time on Oral CAB Study Treatment = last dose date of oral CAB – first dose date of oral CAB + 1
CAB Injection 1 Group in Cohort 3

 If not collected on the eCRF, the dose for injection 1 of Cohort 3 will be derived as follows: If date of injection 1 is prior to 01JAN2021 then dose = 600 mg, otherwise it is 400 mg

10.6.3. Safety

12-Lead Electrocardiograms
General

 Only the average value (for quantitative parameter) or the worst-case value (for interpretation) from the triplicate ECG assessments will be included in the summary statistics, including the maximum QTc values and the maximum increase in QTc values post-baseline relative to baseline summaries.
QTc Interval

 When not entered directly in the eCRF, corrected QT intervals by Bazett's (QTcB) and Fridericia's (QTcF) formulas will be calculated, in msec, depending on the availability of other measurements. 
If RR interval (in msec) is provided, then missing QTcB and/or QTcF will be derived as
 $QTcB = \frac{QT}{\sqrt{RR/1000}} \quad QTcF = \frac{QT}{\sqrt[3]{RR/1000}}$ 
where uncorrected QT interval is also measured in msec.
 
If RR interval is not provided directly and one of QTcB or QTcF has been entered, then RR interval can be obtained from the above formulas and used to calculate the other correction method value; i.e.,
 $QTcB = \sqrt{\frac{QTcF^3}{QT}} \quad QTcF = \sqrt[3]{QT \cdot QTcB^2}$ 
 Average value (for quantitative ECG parameters) and worst-case value (for ECG interpretation) of the triplicate ECG assessments will be used for summaries of ECG change from baseline and ECG interpretations.

- All post-dose assessments will be used to determine the maximum QTc values post-baseline or maximum QTc increase post-baseline.

CCI
CCI

CCI
CCI

Adverse Events

Adverse Events of Special Interest (AESI)

- Please refer to [Appendix 11: AESI Identification](#) for AESI identification

CCI
CCI

CCI

CCI

CCI

10.7. Appendix 7: Reporting Standards for Missing Data

10.7.1. Premature Withdrawals

Element	Reporting Detail
General	
 Withdrawn participants may be replaced in the study. All available data from participants who were withdrawn from the study will be listed and all available planned data will be included in summary tables and figures, unless otherwise specified.

10.7.2. Handling of Missing Data

Element	Reporting Detail
General	
 Missing data occurs when any requested data is not provided, leading to blank fields on the collection instrument: 
 These data will be indicated by the use of a “blank” in participant listing displays. Unless all data for a specific visit are missing in which case the data is excluded from the table. Answers such as “Not applicable” and “Not evaluable” are not considered to be missing data and should be displayed as such.
Outliers	
 Any participants excluded from the summaries and/or statistical analyses will be documented along with the reason for exclusion in the clinical study report.

10.7.2.1. Handling of Missing and Partial Dates

Element	Reporting Detail		
General	
 Partial dates will be displayed as captured in participant listing displays. Where necessary, partial dates may be imputed for specific analysis purposes as outlined below. Imputed partial dates will not be used to derive study day, time to onset or duration (e.g., time to onset or duration of AEs), or elapsed time variables (e.g., time since diagnosis), except for crossover analysis endpoints (see Section 7.5) in which date of last contact will be used to derive duration for ongoing events. 		
Adverse Events	
 Imputations in the AEs dataset are used for slotting events to the appropriate study time periods and for sorting in data listings. Partial dates for AE recorded in the eCRF will be imputed using the following conventions: 
 
 Missing start day	 
 If study treatment start date is missing (i.e. participant did not start study treatment), then set start date = 1st of month. Else if study treatment start date is not missing: 
 If month and year of start date = month and year of study treatment start date then 
 If stop date contains a full date and stop date is earlier than study treatment start date then set start date= 1st of month. Else set start date = study treatment start date. Else set start date = 1st of month. 	
 
 	Missing start day	
 If study treatment start date is missing (i.e. participant did not start study treatment), then set start date = 1st of month. Else if study treatment start date is not missing: 
 If month and year of start date = month and year of study treatment start date then 
 If stop date contains a full date and stop date is earlier than study treatment start date then set start date= 1st of month. Else set start date = study treatment start date. Else set start date = 1st of month.
Missing start day	
 If study treatment start date is missing (i.e. participant did not start study treatment), then set start date = 1st of month. Else if study treatment start date is not missing: 
 If month and year of start date = month and year of study treatment start date then 
 If stop date contains a full date and stop date is earlier than study treatment start date then set start date= 1st of month. Else set start date = study treatment start date. Else set start date = 1st of month. 		

Element	Reporting Detail										
	

Missing start day and month	
• If study treatment start date is missing (i.e. participant did not start study treatment), then set start date = January 1.• Else if study treatment start date is not missing:
○ If year of start date = year of study treatment start date then
▪ If stop date contains a full date and stop date is earlier than study treatment start date then set start date = January 1.▪ Else set start date = study treatment start date.○ Else set start date = January 1.	

Missing stop day	Last day of the month will be used.	

Missing stop day and month	No Imputation	

Completely missing start/end date	No imputation	

 
• Completely missing start or end dates will remain missing, with no imputation applied.	Missing start day and month	
• If study treatment start date is missing (i.e. participant did not start study treatment), then set start date = January 1.• Else if study treatment start date is not missing:
○ If year of start date = year of study treatment start date then
▪ If stop date contains a full date and stop date is earlier than study treatment start date then set start date = January 1.▪ Else set start date = study treatment start date.○ Else set start date = January 1.	Missing stop day	Last day of the month will be used.	Missing stop day and month	No Imputation	Completely missing start/end date	No imputation		
Missing start day and month	
• If study treatment start date is missing (i.e. participant did not start study treatment), then set start date = January 1.• Else if study treatment start date is not missing:
○ If year of start date = year of study treatment start date then
▪ If stop date contains a full date and stop date is earlier than study treatment start date then set start date = January 1.▪ Else set start date = study treatment start date.○ Else set start date = January 1.										
Missing stop day	Last day of the month will be used.										
Missing stop day and month	No Imputation										
Completely missing start/end date	No imputation										
Concomitant Medications	
• Partial dates for any concomitant medications recorded in the eCRF will be imputed using the following convention:

Missing start day	
• If study treatment start date is missing (i.e. participant did not start study treatment), then set start date = 1st of month.• Else if study treatment start date is not missing:
○ If month and year of start date = month and year of study treatment start date then
▪ If stop date contains a full date and stop date is earlier than study treatment start date then set start date= 1st of month.▪ Else set start date = study treatment start date.○ Else set start date = 1st of month.	

Missing start day and month	
• If study treatment start date is missing (i.e. participant did not start study treatment), then set start date = January 1.• Else if study treatment start date is not missing:
○ If year of start date = year of study treatment start date then
▪ If stop date contains a full date and stop date is earlier than study treatment start date then set start date = January 1.▪ Else set start date = study treatment start date.• Else set start date = January 1.	

Missing end day	A '28/29/30/31' will be used for the day (dependent on the month and year)	

Missing end day and month	A '31' will be used for the day and 'Dec' will be used for the month.	

Completely missing start/end date	No imputation	

 
• The recorded partial date will be displayed in listings.	Missing start day	
• If study treatment start date is missing (i.e. participant did not start study treatment), then set start date = 1st of month.• Else if study treatment start date is not missing:
○ If month and year of start date = month and year of study treatment start date then
▪ If stop date contains a full date and stop date is earlier than study treatment start date then set start date= 1st of month.▪ Else set start date = study treatment start date.○ Else set start date = 1st of month.	Missing start day and month	
• If study treatment start date is missing (i.e. participant did not start study treatment), then set start date = January 1.• Else if study treatment start date is not missing:
○ If year of start date = year of study treatment start date then
▪ If stop date contains a full date and stop date is earlier than study treatment start date then set start date = January 1.▪ Else set start date = study treatment start date.• Else set start date = January 1.	Missing end day	A '28/29/30/31' will be used for the day (dependent on the month and year)	Missing end day and month	A '31' will be used for the day and 'Dec' will be used for the month.	Completely missing start/end date	No imputation
Missing start day	
• If study treatment start date is missing (i.e. participant did not start study treatment), then set start date = 1st of month.• Else if study treatment start date is not missing:
○ If month and year of start date = month and year of study treatment start date then
▪ If stop date contains a full date and stop date is earlier than study treatment start date then set start date= 1st of month.▪ Else set start date = study treatment start date.○ Else set start date = 1st of month.										
Missing start day and month	
• If study treatment start date is missing (i.e. participant did not start study treatment), then set start date = January 1.• Else if study treatment start date is not missing:
○ If year of start date = year of study treatment start date then
▪ If stop date contains a full date and stop date is earlier than study treatment start date then set start date = January 1.▪ Else set start date = study treatment start date.• Else set start date = January 1.										
Missing end day	A '28/29/30/31' will be used for the day (dependent on the month and year)										
Missing end day and month	A '31' will be used for the day and 'Dec' will be used for the month.										
Completely missing start/end date	No imputation										

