8.2.6. Assessment of Injection Site Reactions

Injection Site Reaction examination will include an assessment of pain (or tenderness), pruritis, warmth, infections, rash, erythema (or redness), swelling (or induration), and nodules (granulomas or cysts). Digital photographs will be documented on all participants who have an injection site reaction that are considered more serious by the principal investigator (PI), e.g. Grade 2 or above or if persistent beyond 2 weeks.

Injection site erythema/redness or swelling/induration will be evaluated and graded using the greatest measured surface area (as well as impact with usual social and functional activities) as per DAIDS and data regarding the size of these injection site reactions recorded at each ISR assessment. The greatest width and length of these injections site reactions should be recorded in the CRF at each ISR assessment (Cohorts 4, 5 and 6). If the grade of an ISR changes over time, each change will also be recorded in the CRF. See Section [11.7](#) The Division of AIDS Table for Grading the Severity of Adult and Pediatric Adverse Events (“DAIDS AE Grading Table”).

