8.3.3. Follow-up of AEs and SAEs

After the initial AE/SAE report, the investigator is required to proactively follow each participant at subsequent visits/contacts. All SAEs, non-serious AEs such as ISRs, will be followed until the event is resolved, stabilized, otherwise explained, or the participant is lost to follow-up (as defined in Section 7.3). Further information on follow-up procedures is given in Appendix 3.

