No.	Population	GSK Standard/ Example Shell	Title	Programming Notes	Deliverable [Priority]
2.25.	Safety	SAFE_T1 (See EG1)	Summary of ECG Findings – Part 1 & Part 2–	Unscheduled visits are included for determining worst-case post-baseline	Cohort 1-5, EOS
2.26.	Safety	EG2	Summary of ECG Values – Part 1 & Part 2		Cohort 1-5, EOS
2.27.	Safety	EG2	Summary of ECG Changes from Baseline – Part 1 & Part 2		Cohort 1-5, EOS
2.28.	Safety	SAFE_T2 (See EG10A)	Summary of Maximum QTc Values Post-Baseline Relative to Baseline by Category – Part 1 & Part 2	Unscheduled visits are included for determining maximum QTc values	Cohort 1-5 IA Cohort 1-4, Cohort 1-5, EOS
2.29.	Safety	SAFE_T3 (See EG11)	Summary of Maximum Increase in QTc Values Post-Baseline Relative to Baseline by Category – Part 1 & Part 2	Unscheduled visits are included for determining maximum increase in QTc values	Cohort 1-5 IA Cohort 1-4, Cohort 1-5, EOS
Vital Signs					
2.30.	Safety	VS1	Summary of Vital Sign Values - Part 1 & Part 2		
2.31.	Safety	VS1	Summary of Vital Sign Changes from Baseline – Part 1 & Part 2		Cohort 1-5, EOS
2.32.	Safety	SAFE_T4 (See VS3)	Summary of Vital Sign Results Relative to Potential Clinical Importance (PCI) Criteria Post-Baseline Relative to Baseline – Part 1 & Part 2	Unscheduled visits are included for determination of 'to Low' and 'to High'	Cohort 1-5 IA Cohort 1-4, Cohort 1-5, EOS
Liver Events					
2.33.	Safety	LIVER1	Summary of Liver Stopping Event Reporting – Part 1 & Part 2		Cohort 1-5 IA Cohort 1-4, Cohort 1-5, EOS

Safety: Tables					
No.	Population	GSK Standard/ Example Shell	Title	Programming Notes	Deliverable [Priority]
2.34.	Safety	LIVER10	Summary of Hepatobiliary Laboratory Abnormalities – Part 1 & Part 2	Unscheduled visits are included	Cohort 1-5, EOS
Questionnaires					
2.35.	Safety	SAFE_T5	Summary of Numeric Rating Scale – Part 1 & Part 2	For each period: by visit, maximum and AUC. AUC not needed for Cohort 1-5 IA	Cohort 1-5 IA Cohort 1-4, Cohort 1-5, EOS
2.36.	Safety	SAFE_T6	Summary of Perception of Injection – Part 1 & Part 2		Cohort 1-5 IA Cohort 1-4, Cohort 1-5, EOS
Injection Site Area & Duration by Grade					
2.37.	Safety	SAFE_T7a	Event-Level Summary of Duration (Days) at Each Grade by Injection Site Reaction Preferred Term – Part 1 & Part 2	Injection 1 and Injection 2 periods only. Include pooled treatment groups by dose & route	Cohort 1-5 IA Cohort 1-4, Cohort 1-5, EOS

Safety: Tables					

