No.	Population	GSK Standard/ Example Shell	Title	Programming Notes	Deliverable [Priority]
2.38.	Safety	SAFE_T7b	Event-Level Summary of Duration (Days) at Each Grade – Grading determined according to DAIDS Impact on Social and Function Activities Categories and Occurrence of Other Associated Grade 3 ISRs or Potentially Life-Threatening Consequences – Part 1 Cohort 4h	Repeat for each of the following grouped preferred terms: Erythema/Redness/Induration/Swelling, Erythema/Redness, and Induration/Swelling Injection 1 and Injection 2 periods only. Include pooled treatment groups by dose & route	Cohort 1-5 IA Cohort 1-4, Cohort 1-5, EOS
2.39.	Safety	SAFE_T7c	Subject-Level Summary of Maximum Duration (Days) at Each Grade by Injection Site Reaction Preferred Term – Part 1 & Part 2	Injection 1 and Injection 2 periods only. Include pooled treatment groups by dose & route	Cohort 1-5 IA Cohort 1-4, Cohort 1-5, EOS
2.40.	Safety	SAFE_T7d	Subject-Level Summary of Maximum Duration (Days) at Each Grade – Grading determined according to DAIDS Impact on Social and Function Activities Categories and Occurrence of Other Associated Grade 3 ISRs or Potentially Life-Threatening Consequences – Part 1 Cohort 4h	Repeat for each of the following grouped preferred terms: Erythema/Redness/Induration/Swelling, Erythema/Redness, and Induration/Swelling Injection 1 and Injection 2 periods only. Include pooled treatment groups by dose & route	Cohort 1-5 IA Cohort 1-4, Cohort 1-5, EOS

Safety: Tables					
No.	Population	GSK Standard/ Example Shell	Title	Programming Notes	Deliverable [Priority]
2.41.	Safety	SAFE_T8	Subject- CCI 

 

 

	Injection 1 and Injection 2 periods only.	Cohort 1-4, Cohort 1-5, EOS
Crossover Statistical Analyses for Cohort 4b, including summaries of endpoints for other cohorts					
2.42.	Safety – LA Exposed (Complete Case)	SAFE_XO1	Statistical Analysis for Proportion of Participants with Injection Site Reactions – CCI 

 

 

	CCI 

	Cohort 1-5, EOS
2.43.	Safety – LA Exposed (Complete Case)	SAFE_XO2	CCI 

		Cohort 1-5, EOS
2.44.	Safety – LA Exposed (Complete Case)	SAFE_XO3			Cohort 1-5, EOS
2.45.	Safety – LA Exposed (Complete Case)	PIN_XO1			Cohort 1-5, EOS
2.46.	Safety – LA Exposed (Complete Case)	PIN_XO2			Cohort 1-5, EOS

Safety: Tables					
No.	Population	GSK Standard/ Example Shell	Title	Programming Notes	Deliverable [Priority]

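### Under the visible date rule, the still-open grade spell of an unresolved injection-site reaction has no duration in SAP Tables 2.37-2.40, which shortens those summaries at the early data cuts

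*SAP*

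**What the plan says.** SAP 10.7.2.1 sets the general rule: "Imputed partial dates will not be used to derive study day, time to onset or duration (e.g., time to onset or duration of AEs"). It gives one exception: "except for crossover analysis endpoints (see Section 7.5) in which date of last contact will be used to derive duration for ongoing events". For adverse events it adds: "Completely missing start or end dates will remain missing, with no imputation applied".

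SAP 10.10.5 lists the duration displays. Table 2.37 is the "Event-Level Summary of Duration (Days) at Each Grade by Injection Site Reaction Preferred Term" and Table 2.39 the "Subject-Level Summary of Maximum Duration (Days) at Each Grade by Injection Site Reaction Preferred Term", both for Part 1 and Part 2. Tables 2.38 and 2.40 are the Cohort 4h counterparts, graded by impact on activities. All four are due for the Cohort 1-5 interim, Cohort 1-4, Cohort 1-5 and end-of-study deliverables. They come before, and outside, the block headed "Crossover Statistical Analyses for Cohort 4b, including summaries of endpoints for other cohorts".

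Two protocol provisions bear on this. Section 8.2.6 states: "If the grade of an ISR changes over time, each change will also be recorded in the CRF". Section 8.3.3 says that adverse events, naming injection-site reactions among them, "will be followed until the event is resolved, stabilized, otherwise explained, or the participant is lost to follow-up".

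**The concern.** The exception shows that the authors saw the problem: an ongoing event has no duration until it is given an end point. They supplied one only for the crossover endpoints. No visible rule does the same for Tables 2.37-2.40.

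A reaction still open at a data cut tends to be a long one. If its open spell contributes nothing, the summaries describe completed spells only and are too short. The subject-level maximum is the most exposed: when a participant's longest spell is the open one, the maximum falls to a shorter closed spell, or the participant leaves that row.

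The loss also depends on follow-up. SAP 3.2 says that Cohorts 1-3 will have finished follow-up at the Cohort 1-5 interim, while Cohort 4b will not have finished its injection phase. The same reaction could therefore look shorter in a later cohort only because it was observed for less time. Protocol 2.3 names injection-site reactions as the main safety concern, and the 2.3.1 risk table says that the effect of rHuPH20 on them is unknown, so these comparisons will be read closely.

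**Working it through.** The plan gives no figure for this, so there is none to reproduce. The check has two parts.

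**1. Reading the rule.**
- An ongoing reaction has no end date. The adverse-event rule leaves a completely missing end date missing.
- The last-contact exception applies to crossover analysis endpoints. Tables 2.37-2.40 are not in the crossover block.
- Grade changes are recorded, so earlier grade spells of an ongoing reaction can have a start and an end. Only the current spell is open.
- Hence, in the visible text, the open spell has no duration in these four tables.

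**2. Illustrating the size.** Inputs:
- Data cuts of 28 days (shortest follow-up after the last injection for a Part 1 participant who has just completed the injection phase), 56 days (intermediate) and 364 days (52-week follow-up).
- Assumed: exponential whole-event durations with true median m, and onset at injection. The only duration in the documents is a median of under one week for individual events with CAB 200 mg/mL (Protocol 2.3.1).

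With rate λ = ln 2 / m and cut C:
- proportion open: p = exp(−λC)
- true mean: 1/λ
- mean of resolved events only: 1/λ − C·p/(1 − p)
- mean with open events closed at the cut: (1 − p)/λ

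For m = 7 and C = 28: p = 2⁻⁴ = 6.25%; 1/λ = 10.1; resolved only, 10.1 − 28 × 0.0625/0.9375 = 8.2; closed at the cut, 0.9375 × 10.1 = 9.5.

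For m = 14 and C = 28: p = 2⁻² = 25%; 1/λ = 20.2; resolved only, 20.2 − 28 × 0.25/0.75 = 10.9; closed at the cut, 15.1.

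| Cut (days) | True median | Open | Mean, resolved only | Mean, closed at cut | True mean |
|---|---|---|---|---|---|
| 28 | 3 | 0.2% | 4.3 | 4.3 | 4.3 |
| 28 | 7 | 6.3% | 8.2 | 9.5 | 10.1 |
| 28 | 14 | 25% | 10.9 | 15.1 | 20.2 |
| 56 | 14 | 6.3% | 16.5 | 18.9 | 20.2 |
| 364 | 14 | 0.0% | 20.2 | 20.2 | 20.2 |
| 364 | 56 | 1.1% | 76.7 | 79.9 | 80.8 |

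Medians at the 28-day cut move the same way: resolved events only give 6.4 for a true 7 days and 9.5 for a true 14.

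A heavier tail makes the early cut worse. For a lognormal with median 7 and log-scale SD 1.5, 17.8% are open at 28 days and the resolved-only mean is 7.4 against a true 21.5; at 364 days, 0.4% are open.

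The rows for m = 14 also show the comparison problem: identical reactions average 10.9 days in a cohort cut at 28 days and 20.2 in one followed for 364.

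**The case against.** The strongest reply is that exclusion is nowhere stated. Much of SAP 10.6.3 and of Sections 7.4 and 7.5 is redacted, and the four tables use non-standard shells held in separate documents. A rule that counts, censors or closes ongoing reactions may exist there. This stands, and it makes the point conditional. It does not remove the point, because a hidden last-contact rule for these tables would conflict with the single exception in 10.7.2.1.

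Other parts of the reply also stand:
- A reader might infer that the exception stops at Cohort 4b. It is worded for crossover endpoints, and those displays include summaries for other cohorts.
- A reader might infer that a whole ongoing reaction disappears. Recorded grade changes mean that only its current grade spell need be lost, so the whole-event percentages above do not transfer directly to the tables.
- A reader might take an incomplete end date as the mark of a long event. The rule does withhold a duration from a resolved event with a partial stop date, but that says nothing about its length.
- A 28-day cut is close to the worst case. It applies mainly to the most recently injected participants; earlier cohorts have longer follow-up, and the tables are rerun at end of study.
- Long durations have no source in the documents. The higher frequency of nodules and erythema by the subcutaneous route (Protocol 2.3.1) concerns incidence, and those events were described as mild.

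**Conclusion.** The point holds in conditional form. As visibly written, the date rule gives no duration to the open grade spell of an unresolved reaction in Tables 2.37-2.40. If no redacted text or shell overrides it, those summaries are biased downward at the Cohort 1-4, Cohort 1-5 interim and Cohort 1-5 deliverables, most for recently injected participants and for the subject-level maximum. The direction follows from the rule; the size does not. Under the assumed exponential model at a 28-day cut, it runs from nothing visible at a 3-day median, through 8.2 against 10.1 days at a 7-day median, to 10.9 against 20.2 at a 14-day median. The visible documents do not say which statistics the tables report, so these means and medians are illustrations only.

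The documents do not support a claim that the final results will be materially wrong. At 364 days no more than about 1% of events remain open even with a 56-day median, barring loss to follow-up.

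**What to change.** State in SAP 10.7.2.1 how ongoing injection-site reactions enter Tables 2.37-2.40. Apply the existing last-contact convention, or the data cut-off date if that is earlier, to the open grade spell. Flag these durations as censored minimum values, and print the number ongoing beside each summary. If the redacted text or the shells already contain such a rule, a cross-reference from 10.7.2.1 is enough.

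Closing at last contact reduces the bias without removing it: in the 14-day example at 28 days the mean rises from 10.9 to 15.1, still short of 20.2. That is why the flag and the count are needed. A Kaplan-Meier summary is optional and only sensible where cells are large enough; active-control arms have two participants per cohort.

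The cost is a sentence or two of SAP text and minor programming, since the convention already exists for the crossover endpoints. Reported durations will be somewhat longer, and those for ongoing events will still be minimum values.
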